8 STATISTICAL RESULTS

8.1 Sample characterization

Sample characterization results will be presented in table 1 of the appendix.

8.2 Compliance for pre and post intervention period

The results regarding compliance survey of the pre-intervention period (scrub-the-hub) will be presented in table 2, listing 2 and listing 3 of the appendix.

Results regarding the compliance in the post-intervention period (use of the disinfecting barrier cap on needleless connectors) will be presented in table 15 and listing 1 of the appendix.

Results regarding compliance rate comparisons between retrospective and prospective periods will be presented in table 16 of the appendix.

8.3 Infection assessments for the pre and post intervention period

The results regarding the infections assessments in the retrospective period (scrub-the-hub) and in the prospective period (use of the disinfecting barrier cap on needleless connectors) will be presented in tables 3 and 4 and listing 5 of the appendix.

CLABSI/CAUTI/VAP comparisons between pre-intervention and prospective periods will be presented in table 5 of the appendix.

Poisson regression results model for predicting rate of CLABSI infections, and by MBI, will be presented in table 6, table 7, table 8, table 9, table 10 and table 11 of the appendix.

Poisson regression results model for predicting rate of CAUTI infections will be presented in table 12 of the appendix.

Poisson regression results model for predicting rate of VAP infections will be presented in table 13 of the appendix.

8.4 Changes to infection reduction practices

Changes to infection reduction practices will be presented in table 14 and listing 6 of the appendix.

8.5 Brainstorming

Brainstorming results will be presented in table 17 and in listing 4 of the appendix.

8.6 Compliance by format of disinfecting cap

Compliance by format of disinfecting cap (disinfecting cap strips vs. individual disinfecting caps) for the post-intervention period will be presented in table 18 of the appendix.

9 DATA, DERIVATIONS AND TRANSFORMATIONS

- **Scrub-the-hub survey compliance (retrospective period)**

Compliance of the scrub-the-hub (self-reported and coworkers) survey will be calculated through scrub time and dry time:

In each of the scrub time (Table 1) and dry time (Table 2) questions tables a calculation has to be made to provide the percent of the time that the clinician scrubs the hub (Table 1) 10 seconds or more or allows the hub to completely dry (Table 2).

Each answer has a percentage assigned for the calculation of compliance: “Always” = 100%; “Usually” = 75%; “Sometimes” = 25%; and “Never” = 0%.

Only the answers of “≥10 - <15 seconds” and “≥15 seconds” will be considered for the calculation of compliance, because physicians will only be compliant if scrub time is equal or more than 10 seconds. Therefore, in compliance calculation, scrub time for “No scrub”, “<5 seconds”, “≥5 - < 10 seconds” will be multiplied by zero.

For the example bellow (Table 1), compliance of scrub time will be calculated as follow:

$$\begin{array}{r}
 0\% \times 0 \\
 + 25\% \times 0 \\
 + 75\% \times 0 \\
 + 25\% \times 1 \\
 + 0\% \times 1 \\
 \hline
 25\%
 \end{array}$$

The first three rows values would then be multiplied by zero and the last two multiplied by 1. The percentage will then be totaled by summing all the percentages for each scrub time.

Table 1 – Scrub-the-Hub survey (scrub time table)

Scrub Time	Always (100%)	Usually (75%)	Sometimes (25%)	Never (0%)
No scrub				
<5 seconds				
≥5 - <10 seconds				
≥10 - <15 seconds				
≥15 seconds				
If scrub time <10 seconds, indicate the most likely reason:		 The patient urgently needed the medication  High patient - nurse ratio  In my mind, I believe <10 seconds is more than necessary  Another reason: _____		

For dry time, compliance will be calculated as follow:

$$\begin{array}{r}
 75\% \times 0 \\
 + 25\% \times 1 \\
 \hline
 25\%
 \end{array}$$

The first-row value would then be multiplied by zero and the last row multiplied by 1. The percentage will then be totaled by summing all the percentages for the two dry times.

Table 2 – Scrub-the-Hub survey (dry time table)

Dry Time	Always (100%)	Usually (75%)	Sometimes (25%)	Never (0%)
No dry				
Completely dry				

The total compliance for each physician will be calculated through the following formula:

$$\begin{aligned} \text{Scrub – the – hub survey compliance (\%)} \\ = \text{Scrub time compliance (\%)} \times \text{Dry time compliance (\%)} \end{aligned}$$

For the previous example, scrub-the-hub survey compliance rate was: 25% X 25%= **6,25%**

If missing data are present in scrub-the-hub survey, compliance will not be calculated for that subject.

Compliance rate will be calculated per physician.

- **Compliant clinician in scrub-the-hub survey (target compliance rate achieved)**

A dichotomous variable (yes/no) will be calculated.

Yes – clinician who meet compliance rate equal or higher than 70% in scrub-the-hub survey.
No – Otherwise

- **Compliance rate for use of the disinfecting barrier cap on needleless connectors (post-intervention period)**

The following formula must be considered for each shift and ward:

$$\begin{aligned} \text{Compliance rate for use of disinfecting barrier cap on needleless connectors (\%)} = \\ = \frac{\text{No. of applicable capped ports (correctly used)}}{\text{No. applicable capped ports (correctly used)} + \text{No. applicable uncapped ports} + \text{No. applicable ports with missed caps}} \times 100 \end{aligned}$$

If missing data are present in data compliance audits, for a shift/ward then that compliance will not be calculated for that shift/ward.

- **CLABSI rate per 1000 catheter/days**

The following formula must be considered:

$$\begin{aligned} \text{CLABSI rate per 1000 catheter line/days} \\ = \frac{\text{Number of CLABSIs infections}}{\text{Number of central venous catheter (CVC) days}} \times 1000 \end{aligned}$$

- **CAUTI rate per 1000 catheter/days**

The following formula must be considered:

$$\begin{aligned} & \text{CAUTI rate per 1000 catheter/days} \\ &= \frac{\text{Number of CAUTIs infections}}{\text{Number of indwelling urinary catheter days}} \times 1000 \end{aligned}$$

- **VAP rate per 1000 ventilator/days**

The following formula must be considered:

$$\text{VAP rate per 1000 ventilator/days} = \frac{\text{Number of VAPs infections}}{\text{Number of ventilator days}} \times 1000$$

- **Treatment**

A dichotomous variable will be calculated for CLABSI infections time period assessment.

Scrub-the-hub protocol – CLABSI infections detected during the first 6 months, pre-intervention period (retrospective period).

Disinfecting barrier cap – CLABSI infections detected during the last 6 months, post-intervention period (prospective period).

- **Compliance by format of disinfecting cap**

Compliance of disinfecting cap strips will be calculated using the previous formula “*Compliance rate for use of the disinfecting barrier cap on needleless connectors (post-intervention period)*” just with the ICU unit data.

Compliance of individual disinfecting cap will be calculated using the previous formula “*Compliance rate for use of the disinfecting barrier cap on needleless connectors (post-intervention period)*” using data of the following unit wards: 2^o floor, 3^o floor, 3^o floor – surgical ward, 4^o floor and 5^o floor.

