7.2 Compliance Analyses

Compliance rates to scrub-the-hub disinfection procedures before the intervention will be determined by written survey. The target survey response rate on scrub-the-hub compliance is 70% of healthcare professionals in the intervention wards that utilize needleless connectors for patient IV access. An overall compliance rate and compliance rates per intervention ward will be determined.

The calculation method of the survey compliance rate is presented in section 9 - Data, derivations and transformations. Survey compliance will be assessed by the *scrub time* and *dry time* of the self-reported part of the survey.

Compliance rate for the use of the disinfecting barrier cap on needleless connectors during the intervention recording period will be determined by weekly observations in each assigned intervention ward, which will be scheduled to ensure the absence of a shift bias.

The calculation method of the use of the disinfecting barrier cap on needleless connectors compliance is presented in section 9 - Data, derivations and transformations.

Survey compliance rate and compliance rate for the use of the disinfecting barrier cap on needleless connectors during the intervention recording period by wards will also be assessed.

The Student's t-test for independent samples will be used to compare the compliance rate between pre and post intervention period. In case of no evidence of normality assumptions, the Mann-Whitney U test will be used instead of Student's t-test.

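### The baseline scrub score adds two separately rated rows without a cap, so a percentage of time can reach 200%; the survey's missing-data rule is also wider than the score needs

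*SAP*

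**What the plan says.** SAP section 9 derives the scrub-the-hub score for each survey respondent. The answers Always, Usually, Sometimes and Never are worth 100%, 75%, 25% and 0%. The aim of the scrub-time calculation is "to provide the percent of the time that the clinician scrubs the hub (Table 1) 10 seconds or more". For the five scrub-time rows, "The first three rows values would then be multiplied by zero and the last two multiplied by 1", and then "The percentage will then be totaled by summing all the percentages for each scrub time". Dry time has one scored row, Completely dry; No dry is multiplied by zero. The total is scrub time multiplied by dry time.

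On missing answers, section 9 says: "If missing data are present in scrub-the-hub survey, compliance will not be calculated for that subject". It describes the survey as having two parts: "Compliance of the scrub-the-hub (self-reported and coworkers) survey will be calculated through scrub time and dry time". SAP section 7.2, however, assesses compliance on the scrub time and dry time "of the self-reported part of the survey".

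The score is used in two ways. Section 9 defines a compliant clinician as a "clinician who meet compliance rate equal or higher than 70% in scrub-the-hub survey". In section 7.2, a t-test, or a Mann-Whitney test if normality is not supported, "will be used to compare the compliance rate between pre and post intervention period". The other side of that comparison is the audit rate, calculated for each shift and ward.

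**The concern.** The formula does not guarantee the quantity it is said to produce. The form in protocol section 8.1 asks for a separate rating of each scrub-time band. It does not tell respondents that the bands should add up to all of their accesses. A respondent who ticks Usually for both bands of 10 seconds or more gets a scrub score of 150%. The audit rate cannot exceed 100%, because its numerator is part of its denominator.

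This score is the only pre-intervention measure in the primary comparison. Excess values would enter the t-test through the baseline mean and variance. In the Mann-Whitney test they would enter through rank, where a survey total above 100% outranks a perfect audit. If the rule is not set in advance, someone will have to decide what to do with a value such as 112.5% after seeing the data.

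The missing-data wording raises a separate, smaller question. Four of the seven self-reported rows are always multiplied by zero, yet a blank in one of them would void the score on a literal reading. So might a blank on the coworker page.

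**Working it through.** **Inputs.** The weights 100, 75, 25 and 0%, the row multipliers (0, 0, 0, 1, 1 for scrub; 0, 1 for dry) and the product rule come from SAP section 9. The row counts come from the survey in protocol section 8.1: 5 scrub rows + 2 dry rows = 7 per page, and 14 over two pages.

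**The SAP's own example.** Scrub: 0×0 + 25×0 + 75×0 + 25×1 + 0×1 = 25%. Dry: 75×0 + 25×1 = 25%. Total: 25% × 25% = 6.25%, as the SAP states. The five scrub rows in this example add up to 0 + 25 + 75 + 25 + 0 = 125%, so the SAP itself scores a survey whose rows do not add to 100%. Its score stays in range because only 25 of those 125 points lie in the scored rows.

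**Scrub sum.** With *a* and *b* the two scored rows, there are 4 × 4 = 16 pairs. Six exceed 100%:

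| Pair (either order) | Sum | Pairs |
|---|---|---|
| Always + Always | 200% | 1 |
| Always + Usually | 175% | 2 |
| Usually + Usually | 150% | 1 |
| Always + Sometimes | 125% | 2 |

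**Total score.** With *d* the Completely dry row, there are 4³ = 64 patterns. Compare (a + b) × d with min(100%, a + b) × d.

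- 10 totals exceed 100%, from 112.5% (Usually in all three rows: 150% × 75%) to 200%. After the cap, 4 become 75% and 6 become 100%.
- 18 totals change under the cap (6 pairs × 3 non-zero dry answers). The change runs from 6.25 points (125% × 25% = 31.25% against 25%) to 100 points (200% against 100%).
- 8 of those 18 have an uncapped total of 100% or less. For example, Always + Sometimes with dry Usually gives 125% × 75% = 93.75%, against 75% when capped. Checking only whether the final total exceeds 100% would miss these.

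**70% classification.** 22 of 64 patterns qualify with or without the cap, and none changes. The reason is simple. When the scrub sum exceeds 100%, the capped total equals the dry value. At a dry value of 75% or 100%, both versions pass. At 25%, even the uncapped maximum is 200% × 25% = 50%, so both fail.

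These are counts of possible answer patterns, not expected frequencies of respondents.

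**Missing rows.** The documents give no blank rate. Assume blanks occur independently with probability *q* per row. The share of surveys voided is 1 − (1 − q)^k, where *k* is the number of rows that can void the score. For example, 1 − 0.98⁷ = 13.2%.

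| q | k = 3 (scored rows) | k = 7 (self-reported page) | k = 14 (both pages) |
|---|---|---|---|
| 1% | 3.0% | 6.8% | 13.1% |
| 2% | 5.9% | 13.2% | 24.6% |
| 5% | 14.3% | 30.2% | 51.2% |

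The avoidable loss under the 7-row reading is the difference from the first column: 3.8, 7.3 and 15.9 percentage points.

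**The case against.** The strongest reply is that adding the rows is the right operation. The two bands are mutually exclusive, so their sum is the wanted percentage for any coherent respondent, and the weights fit that idea (Usually + Sometimes = 75 + 25 = 100). A sum above 100% needs contradictory answers, and 200% needs Always in two exclusive bands. On this view the gap is only a missing rule for incoherent answers. Their frequency is unknown, their effect works against the device, and they never alter the 70% classification. The SAP also reports minimum and maximum, so a score above 100% would be noticed.

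Much of this stands. Summation is sound for coherent answers, the direction is conservative, and no frequency can be given. Even so, the form does nothing to secure coherence, and the SAP's own example is not coherent across its five rows. A printed maximum would not reveal the 8 inflated patterns at or below 100%, and noticing the others after the fact does not say how to handle them. On the rank test, the cap has a limited effect for 6 of the 10 patterns: they move from above a perfect audit to level with it.

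On missing data, section 7.2 favours a reading confined to the self-reported page, so the 14-row column is the less likely case. The blank rates are illustrative.

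It is also fair that a cap does not resolve contradictory answers. Usually at 5 to under 10 seconds together with Usually in one band of 10 seconds or more would pass unnoticed. Rescaling by the five-row total or querying respondents would go further. The cap is the smallest change that keeps the score within its definition.

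**Conclusion.** The concern holds and should be fixed before analysis. As written, the rule can return impossible values for the baseline side of the primary endpoint: 6 of 16 scored pairs exceed 100%, as do 10 of 64 totals, and 18 of 64 totals are inflated. The inflation can only raise the baseline mean and so tends to understate a pre-post gain. Its actual size depends on how many respondents give such answers, which the documents do not show.

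The missing-data point is secondary. It rests on a literal reading, its size depends on an assumed blank rate, and the direction of any effect on the baseline is unknown.

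CRF Version 6 and the external table and listing shells were not available. An edit check there cannot be excluded.

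**What to change.** Make two changes in SAP section 9.

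1. State that scrub time compliance (%) = min(100%, sum of the two rows of 10 seconds or more), applied before multiplying by dry time. List the respondents whose sum exceeded 100%, because the cap bounds the score without settling what they meant. Capping only the final total would not be enough.
2. State that the self-reported score is missing only if one of its three scored rows is blank: the two rows of 10 seconds or more, or Completely dry. Blanks in zero-weighted rows, reason items or the coworker page do not void it. Report the number of surveys not scored.

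If the CRF already rejects contradictory answers, cite that check in the SAP.

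The cost is two sentences, a few lines of derivation code, one listing (which may fit within the survey listings already planned) and one count. No new data are needed. The worked example stays at 6.25%, and the cap can only lower a baseline score or leave it unchanged.

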8.1 Retrospective Compliance Survey

Retrospective Compliance Survey for Scrub the Hub (page 1 of 2)

Date of survey:

Year			Month		Date

Healthcare Professional Name:

During the last 6 months, how have **you** performed the following practices before accessing IV ports.

Scrub Time	Always	Usually	Some-times	Never
No scrub				
< 5 seconds				
≥5 - < 10 seconds				
≥10 - ≤ 15 seconds				
> 15 seconds				

Dry time	Always	Usually	Some-times	Never
No dry				
Completely dry				

What is the standard in your institution?

Scrub time: _____

Whenever you had less than 10 seconds of scrub time, which of the following was most likely to be your reason? (check all that apply)

- The patient urgently needed the medication
- High patient – nurse ratio.
- In my mind, I believe 10 seconds is more than necessary.
- Another reason (text field) _____

[name]

Retrospective Compliance Survey for Scrub the Hub (page 2 of 2)

During the last 6 months, how have you observed **coworkers** performing the following practices (including CRNAs, anesthesia, nursing students, PACU staff, everybody you have observed accessing IV ports)

Scrub Time	Always	Usually	Some-times	Never
No scrub				
< 5 seconds				
≥5 - < 10 seconds				
≥10 - ≤ 15 seconds				
> 15 seconds				

Dry time	Always	Usually	Some-times	Never

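### SAP 9 scores baseline compliance as scrub % times dry %, an unstated independence assumption that the survey cannot test and that can misplace a clinician's score by up to 18.75 points in either direction

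*SAP*

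**What the plan says.** Compliance with hub disinfection is the primary endpoint (Protocol 3.1.1, SAP 2.2). Its baseline side comes from the written survey in Protocol Appendix 8.1, which asks "how have you performed the following practices before accessing IV ports" and then gives one table for scrub time and another for dry time. No item asks how often both were done at the same access, or how often the hub dried after an adequate scrub.

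SAP 9 sets the scoring. "Each answer has a percentage assigned for the calculation of compliance": Always 100%, Usually 75%, Sometimes 25%, Never 0%. Each table is reduced to a "percent of the time that the clinician scrubs the hub (Table 1) 10 seconds or more or allows the hub to completely dry (Table 2"). For scrub time, "The first three rows values would then be multiplied by zero and the last two multiplied by 1", and the rows are summed. For dry time, "The first-row value would then be multiplied by zero and the last row multiplied by 1". The two results are then multiplied: "The total compliance for each physician will be calculated through the following formula", with the worked example "For the previous example, scrub-the-hub survey compliance rate was: 25% X 25" percent. The product also feeds a yes/no variable, where yes means a "clinician who meet compliance rate equal or higher than 70% in scrub-the-hub survey".

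SAP 7.2 compares this score with audited cap compliance by t-test or Mann-Whitney test. The audit measure in SAP 9 is one observed ratio of ports, with no multiplication.

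**The concern.** Compliance with scrub-the-hub is naturally read as doing both steps at an access. The documents do not define it in those words, but combining the two scores by multiplication implies it. Two separate frequencies do not determine how often both happen together, and multiplying them fills that gap with an assumption of independence that neither document states.

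The assumption may well fail. Two of the survey's listed reasons for a short scrub, urgent medication and a high patient-nurse ratio, are time pressures that could also cut drying at the same access. Baseline would then be scored too low and the gain credited to the cap too large. The assumption touches only the pre-intervention side of the primary comparison, and the collected data cannot test it.

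**Working it through.** **Inputs.** The answer weights, the two qualifying scrub rows, the single qualifying dry row, the product rule and the 70% cut-off are all from SAP 9. Let s be the scrub score and d the dry score.

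**The plan's own figure.** In the SAP example s = 25% + 0% = 25% and d = 25%. The product is 0.25 × 0.25 = 0.0625, or 6.25%, as printed.

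**What s and d allow.** For scores of at most 100%, the share of accesses with both steps done lies between max(0, s + d - 100%) and min(s, d). The upper limit means that the less frequent step occurs only at accesses where the other is also done.

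| Scrub / dry | Product | Lower bound | Upper bound | Upper minus product | Product minus lower |
|---|---|---|---|---|---|
| Sometimes / Sometimes (25, 25) | 6.25% | 0% | 25% | 18.75 | 6.25 |
| Usually / Sometimes (75, 25), either order | 18.75% | 0% | 25% | 6.25 | 18.75 |
| Usually / Usually (75, 75) | 56.25% | 50% | 75% | 18.75 | 6.25 |
| Always / Usually (100, 75) | 75% | 75% | 75% | 0 | 0 |

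A scrub score of 50% (Sometimes on both qualifying rows) gives 12.5 points on either side: with d = 75%, product 37.5% and bounds 25% to 50%; with d = 25%, product 12.5% and bounds 0% to 25%. So 18.75 points is the largest possible error in each direction. If either score is 0% or 100%, the bounds meet and the product is exact.

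**Partial association.** With an assumed within-clinician correlation r between the steps, the joint share is sd + r√(s(1-s)d(1-d)). For both equal pairs the root term is 0.75 × 0.25 = 0.1875.

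| r (assumed) | Sometimes / Sometimes | Usually / Usually |
|---|---|---|
| 0 | 6.25% | 56.25% |
| 0.25 | 10.9% | 60.9% |
| 0.5 | 15.6% | 65.6% |
| 0.75 | 20.3% | 70.3% |
| 1 | 25% | 75% |

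A Usually/Usually clinician reaches 70% at r = (0.70 - 0.5625) / 0.1875 = 0.73. Among the pairs in the first table, this is the only one whose yes/no classification depends on the assumption.

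**Scrub scores above 100%.** SAP 9 sums the two qualifying rows without a limit. Usually on both gives 75% + 75% = 150%. With d = 75% the product is 112.5%, and the bounds come out reversed: lower 150 + 75 - 100 = 125%, upper 75%. With d = 25% the product is 37.5%, although the joint share cannot exceed 25%. Limiting s to 100% gives 75% and 25% respectively, with both bounds equal to the product.

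**The case against.** **The direction is not established.** The listed reasons are asked only about scrubs under 10 seconds. One of them, the belief that 10 seconds is more than necessary, gives no reason to skip drying. Nothing in the documents measures the association. This stands: positive association is plausible, not shown, and the bounds extend below the product as well as above it.

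**Drying may have been rated given a scrub.** Drying has little meaning at an access with no scrub. If respondents rated drying after an adequate scrub, the product is the exact joint share. The wording of SAP 9 leans towards an unconditional percentage, but the survey does not settle how respondents read the question. If they meant drying after any scrub, the product still assumes that long and short scrubs are dried equally often.

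**A reader might infer that the rule lowers baseline for every clinician who answers less than Always on both steps, so that the primary comparison is biased towards the cap.** The documents do not support this. The product is exact when a score is 0% or 100%, and Usually plus Sometimes on the scrub rows already makes 100%. The unlimited sum can push scores above what is possible, and self-report may also inflate them. No distribution of answers is given, so the effect on the mean cannot be calculated.

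**A reader might also infer that min(scrub, dry) should replace the product in the primary analysis.** That would exchange independence for complete dependence, which is equally untested and more extreme. The bound belongs in a sensitivity analysis.

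**Conclusion.** The concern holds in a limited form. The baseline score depends on an unstated and untestable assumption whenever both component scores lie strictly between 0% and 100%. For such a clinician the product can be too low by up to 18.75 points if the steps go together, or too high by up to 18.75 points if they are negatively associated. In the first case the apparent gain with caps is enlarged, and a Usually/Usually clinician can be wrongly classed as not compliant. These sizes rest on the SAP's assigned weights, on reading the dry rating as unconditional, and on compliance meaning both steps at the same access. They are limits for single answer patterns, not estimates of bias in the mean; the size and sign of that bias are unknown. What is affected is how firmly a pre/post gain can be stated, particularly a modest one.

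**What to change.** In SAP 9 and 7.2:

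1. Limit the scrub score to 100% before any further calculation. Without this the bounds can reverse.
2. Keep the product as the planned score, and state that it assumes scrubbing and drying are unrelated across accesses, or that drying was rated given an adequate scrub.
3. Derive for each clinician the upper bound min(scrub %, dry %) and the lower bound max(0, scrub % + dry % - 100%). Prespecify both as sensitivity analyses for the pre/post comparison and for the 70% classification.
4. State that a compliance gain will be called robust to this assumption only if it holds against the upper bound.

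The cost is a few lines of SAP text and two derived variables, with no new data. The downside is that the gain reported against the upper bound may be smaller.
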